## 5.2 Dose Modifications and Dosing Delays

The following dose modification rules will be used with respect to potential toxicity. Toxicity will be assessed according to the NCI CTCAE version 5.0.

The following dose modifications should be made for febrile neutropenia, and blood counts obtained on day one of each cycle. If more than one of these conditions applies, use the most stringent (i.e., the greatest dose reduction). **The AE may be due to pembrolizumab or vorinostat alone in which case the respective agent should be reduced. If overlapping toxicity is suspected, both drugs may be reduced with the potential to re-escalate the non-offending agent. Given the very different nature of pembrolizumab and vorinostat/tamoxifen toxicities, separate tables are shown for individual agents.**

**No dose modification will be pursued for tamoxifen.**

**Hematologic Toxicity\***

**Adverse Event:\* Neutropenia**

While dose hold may apply for all days of occurrence, dose modification will only apply if neutropenia persists for day 1, 8, and 15 of each cycle. Dose modifications are not required if labs are drawn on other days and counts have recovered upon retreatment on days 1, 8, 15.

Neutropenia Febrile neutropenia	Management/Next Dose for Vorinostat
ANC $\geq$ 1000	100%
ANC: 500-1000	Hold for until $\leq$ grade 2 #, Restart at 75%: 300 mg qd for all subsequent cycles Second occurrence resume at 200 mg qd for all subsequent cycles Third occurrence: remove from study
ANC: 0-500	Hold for until $\leq$ grade 2 or less# Restart at 75%: 300 mg qd for all subsequent cycles Second occurrence resume at 200 mg qd for all subsequent cycles Third occurrence: discuss with sponsor and principal investigator, consider omitting alternate weeks

#Patient with a dose delay for more than 3 weeks in the first 2 cycles will need to be replaced for toxicity and efficacy assessments.

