### 3.2 Sample Size

We adopt a randomized two-arm trial with futility early stopping built-in within each treatment arm using a Simon's two-stage design (Simon, 1989). The effect of vorinostat on pembrolizumab and the effect of pembrolizumab and tamoxifen in this biomarker-selected population of ER+ breast cancer patients will be first tested against the respectively chosen null rate in the first stage within the treatment arms and then compared between the treatment arms.

65 patients to be treated under the study/enrolled in the investigational portion of the study (sample size for primary objective).

**For Arm A (vorinostat + TAM + pembro):** The null hypothesis that the true response rate for pembrolizumab and vorinostat in ER+ pretreated patients alone without biomarker enrichment is 0.15 which will be tested against the alternative that response rate of pembrolizumab in a biomarker select population is 0.40. In the first stage, 13 patients will be accrued. If there are 2 or fewer responses in these 13 patients, the study will be stopped. Otherwise, 22 additional patients will be accrued for a total of 35. The null hypothesis will be rejected if 10 or more responses are observed in 35 patients. This design yields a type I error rate of 0.025 and power of 0.9 in this treatment arm when the true response rate is 0.4 in this patient subpopulation.

**For Arm B (pembro + TAM):** The null hypothesis that the true response rate for pembrolizumab in ER+ pretreated patients alone is 0.10 which will be tested against the alternative that response rate of pembrolizumab in a biomarker select population is 0.35. In the first stage, 11 patients will be accrued. If there are 1 or fewer responses in these 11 patients, the study will be stopped. Otherwise, 19 additional patients will be accrued for a total of 30. The null hypothesis will be rejected if 7 or more responses are observed in 30 patients. This design yields a type I error rate of 0.025 and power of 0.9 in this treatment arm when the true response rate of pembro + TAM treatment is 0.35 in this patient subpopulation.

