#### 3.3.1 Inclusion Criteria

1. Pre and postmenopausal women or men with stage IV ER+ breast cancer histological or cytological confirmation, 18 years of age or older.

Because no dosing or adverse event data are currently available on the use of pembrolizumab, vorinostat, or tamoxifen in patients <18 years of age, children are excluded from this study but will be eligible for future pediatric trials.

2. >10% expression of PD-1/CTLA-4 dual staining in CD8 cells in tumor or blood or  $\geq 5\%$  expression of PD-1/CTLA-4 dual staining in CD4 in blood (only).
3. Eastern Cooperative Oncology Group (ECOG) Performance Status of  $\leq 1$ .
4. Understand and voluntarily sign an informed consent prior to any study-related assessments or procedures are conducted and are able to adhere to the study visit schedule and other protocol requirements.
5. Consent to paired tumor biopsy
6. Measurable tumor by RECIST criteria
7. Per Good Clinical Practice, any toxicity related to prior therapies that, in the opinion of the investigator, would potentially be worsened with anti-PD1 therapy should be resolved to less than Grade 1
8. Adequate organ function:
  - Absolute neutrophil count (ANC)  $\geq 1.5 \times 10^9/L$
  - Hemoglobin (Hgb)  $\geq 9g/dL$  (may transfuse if clinically indicated)
  - Platelets (plt)  $\geq 100 \times 10^9/L$
  - Potassium within normal range, or correctable with supplements;
  - AST and ALT  $\leq 2.5 \times$  Upper Limit Normal (ULN) or  $\leq 5.0 \times$  ULN if liver tumor is present;
  - Serum total bilirubin  $\leq 1.5 \times$  ULN
  - Serum creatinine  $\leq 1.5 \times$  ULN, or 24-hr clearance  $\geq 60ml/min$ ; and
9. Females of childbearing potential (defined as sexually mature women who):
  - Has not undergone a hysterectomy (the surgical removal of the uterus) or bilateral oophorectomy (the surgical removal of both ovaries) or,
  - Has not been naturally postmenopausal for at least 24 consecutive months (i.e., has had menses at any time during the preceding 24 consecutive months) must have
    - Negative serum pregnancy test within 14 days before starting study treatment in females of childbearing potential (FCBP) and willingness to adhere to acceptable forms of birth control (a physician-approved contraceptive method (oral, injectable, or implantable hormonal contraceptive; tubal ligation; intra-uterine device; barrier contraceptive with spermicide; or vasectomized partner)

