**Adverse Event: Anemia**

Hemoglobin	Management/Next Dose for Vorinostat
>8 mg/dl	100 %: 400 mg qd
6.5-8 mg/dl	75 %: 300 mg qd
<6.5 mg/dl	50 %: 200 mg qd

An alternative to dose modification in cases of anemia only would be the use of PRBC transfusion.

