**Adverse Event: Thrombocytopenia**

While dose hold may apply for all days of occurrence, dose modification will only apply if thrombocytopenia persists for day 1, 8, and 15 of each cycle. Dose modifications are not required if labs are drawn on other days and counts have recovered upon retreatment on days 1, 8, 15.

Platelets	Management/Next Dose for Vorinostat
>75'000	100 %: 400 mg qd
<75'000	100 %: 400 mg qd
$\leq$ 50'000/mm 	Hold until $\leq$ grade 2 or less Restart at 75%: 300 mg qd for all subsequent cycles Second occurrence resume at 200 mg qd for all subsequent cycles Third occurrence: discuss with sponsor and principal investigator, consider omitting alternate weeks
$\leq$ 25'000/mm 	Hold until $\leq$ grade 2 or less Restart at 75%: 300 mg qd for all subsequent cycles Second occurrence resume at 200 mg qd for all subsequent cycles Third occurrence: remove from study

An alternative to dose modification in cases of anemia only would be the use of PRBC transfusion.

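### The neutropenia and thrombocytopenia notes allow a vorinostat reduction only on a three-day condition that scheduled counts cannot show, and they contradict the day-one rule above them

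*Combined protocol and SAP*

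**What the plan says.** The lead-in to Section 5.2 sets the general trigger: "The following dose modifications should be made for febrile neutropenia, and blood counts obtained on day one of each cycle".

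The neutropenia part then has a note of its own. It allows a hold on any day of occurrence but adds that "dose modification will only apply if neutropenia persists for day 1, 8, and 15 of each cycle". Its second sentence reads: "Dose modifications are not required if labs are drawn on other days and counts have recovered upon retreatment on days 1, 8, 15". The thrombocytopenia part says the same for platelets ("dose modification will only apply if thrombocytopenia persists for day 1, 8, and 15 of each cycle") and repeats the second sentence. The anemia table has no such note.

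The tables act on an ANC below 1000 and on platelets of 50,000 or less. Both direct a hold until grade 2 or better, then "Restart at 75%: 300 mg qd for all subsequent cycles", with 200 mg at a second occurrence. A third occurrence means removal from study in one row of each table (ANC 500-1000; platelets of 25,000 or less). In the other row it means discussion with the sponsor and principal investigator. The rows do not repeat the three-day condition.

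Section 8.2 leaves vorinostat adjustment in individual patients to these guidelines.

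**The concern.** As worded, the note is a restriction with three parts that must all be met: a low count on day 1, on day 8 and on day 15. If the study calendar does not provide counts on those days, and the drug is stopped in the meantime, the reduction in the table has almost no route to being applied. The lead-in, on the same page of rules, would apply it on a day-one count alone.

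At stake is the dose at which a patient restarts after a severe cytopenia. The table carries that dose into every later cycle. Whether the event counts as an occurrence also matters, because the second and third occurrences bring larger reductions and possible removal from study.

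**Working it through.** No stated figure is in question, so the check sets the required count days beside the scheduled ones and then follows one patient through each rule.

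**Scheduled counts.** Section 6.1 and the visit lists in Sections 6.3.1.1 to 6.3.2.5 place a CBC at screening, C1D1, C1D15, C2D1 and day 1 of later cycles.

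| Day named in the note | Cycle 1 | Cycle 2 onward |
|---|---|---|
| 1 | scheduled | scheduled |
| 8 | none | none |
| 15 | scheduled | none |
| Covered | 2 of 3 | 1 of 3 |

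Visit windows do not close the gap. Section 6 gives ±5 days and the calendar ±3, so the C1D15 count could move back to day 15 − 5 = 10 or day 15 − 3 = 12, not to day 8. The cycle 1 day 10-12 visit could reach day 8 within ±3 days, but it lists only PK, lymphocyte subset and PBMC samples.

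**Unscheduled counts.** These are allowed, and a hold until recovery needs them. They make the literal condition possible but rarely met:

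- In cycle 1, the day 1 count precedes any vorinostat, in a patient who qualified under Section 3.3.1 with ANC of at least 1.5 and platelets of at least 100 × 10⁹/L.
- In later cycles, the count must stay low from day 1 to day 15 with the drug held. At 4 doses a week, two full weeks missed is 4 × 2 = 8 of the cycle's 4 × 3 = 12 doses, before day 15 is reached.

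**One patient, three readings.** ANC is 400 on C3D1 and has recovered by day 8; this is a first event.

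| Rule applied | Restart dose |
|---|---|
| Note, taken literally | 400 mg (not low on days 8 and 15, so no modification) |
| Lead-in plus table | 300 mg |
| Note, read as still low on a retreatment day | 300 mg |

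So even an ANC in the table's lowest row on day 1 brings no reduction under the literal note.

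**Size of the dose difference.**

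- Table arithmetic: 0.75 × 400 = 300 mg, as the plan states.
- First event, per full cycle: 12 × 400 = 4,800 mg versus 12 × 300 = 3,600 mg, a 25% difference.
- Second event of the same kind: the literal note has counted no earlier occurrence, so 400 mg versus 200 mg. That is 4,800 mg versus 12 × 200 = 2,400 mg per cycle, a 50% difference.

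**The case against.** The best defence is that the note's two sentences should be read together. The second excuses low counts on other days that have recovered by retreatment on day 1, 8 or 15. That implies a reduction when the count is still low on a retreatment day. Vorinostat is given in weekly blocks, the literal reading nearly empties the table, and a single-site team is unlikely to adopt it. This is probably the intent. It does not cure the text, because the first sentence says *only*, *persists* and *and*.

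The lead-in's instruction to use the most stringent rule does not help either. It covers several toxicities occurring together, not which trigger governs one of them.

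A reader might also infer that the lead-in forbids a reduction for a low count on C1D15, for example ANC 800 on that day with recovery by C2D1, so that even the retreatment-day reading conflicts with it. That is weak. The lead-in does not say that only day-one counts matter, and a specific note naming days 8 and 15 can supplement it. The clear contradiction is between the literal note and the lead-in for a low day 1 count.

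Nor do the documents support sizing the problem from the pilot's grade 3-4 thrombocytopenia rate (2 of 34, Section 1.3.1.2). That rate counts patients who had the event, not patients whose restart dose would differ. The latter depends on the timing of low counts and of recovery, which the documents do not report. They give no neutropenia rate at all.

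**Conclusion.** Wrong as written, and minor. The literal condition cannot be shown by scheduled counts in any cycle, would rarely be met with extra counts, and contradicts the lead-in for a low day 1 count. The likely intent can be inferred but is not stated.

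A reader might infer that patients could be re-exposed while still at grade 3-4. The documents do not support that, since every reading holds vorinostat until recovery. The effect is confined to Arm A and to the restart dose (300 versus 400 mg, then 200 versus 400 mg) and the occurrence count. Few patients are likely to be involved; how many cannot be estimated and could be none. No sample size, error rate or endpoint figure changes.

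The per-cycle totals assume a full cycle of 12 doses with no further hold.

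**What to change.** In the neutropenia and thrombocytopenia notes, keep the opening clause about holds and replace the rest of the first sentence with:

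*Dose modification applies if, after vorinostat has been started, the ANC is below 1000 [thrombocytopenia note: platelets are 50,000 or less] on any planned retreatment day (day 1, 8 or 15). One continuous episode, from the first low count until recovery to grade 2 or less, counts as one occurrence.*

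Keep the second sentence of each note, so that a low count on another day that has recovered by the retreatment day needs a hold but no reduction. In the neutropenia note, add that the febrile neutropenia rule is unchanged. In the lead-in, after the reference to day-one counts, add: *except neutrophils and platelets, for which the notes to those tables apply*. Anemia then stays on day 1 counts.

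Two parts of this wording guard against new errors. The words about vorinostat having been started prevent a reduction on a pre-treatment C1D1 count. The episode definition prevents an ANC of 800 on days 1, 8 and 15 from counting as three occurrences and so leading to removal from study.

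The cost is a protocol wording change. No scheduled CBC is added, because a hold until recovery already needs repeat counts. A few more patients may be reduced to 300 mg than under the literal note. The sponsor should confirm that giving up the three-day condition matches its intent.

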### **3.5 Duration of Treatment**

Eligible patients will receive treatment as described above, in consecutive 3-week cycles, until progression of disease or unacceptable toxicity. Patients are expected to receive treatment for at least 3 cycles, at which time the first evaluation for efficacy will occur. If there is continued safety and tolerability, treatment may continue.

All patients will be restaged during at 9 weeks ( $\pm 1$  week) and 18 weeks ( $\pm 1$  week) via imaging scans; staging will then be continued every 3 cycles until 6 months. After 6 months, staging may be spaced out to 6 cycles if clinically indicated.

Patients will be followed for evaluation of safety for at least 30 days after the last dose of study drug. Any study drug-related serious adverse events will be followed until resolution, return to baseline grade, or deemed irreversible by the Investigator.

Subjects who experience a recurrence of the same severe or life-threatening event at the same grade or greater with re-challenge of pembrolizumab should be discontinued from trial treatment.

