#### Formulation, Appearance, Packaging, and Labeling

Vorinostat is supplied as size 3 100 mg capsules for oral administration. Vorinostat will be supplied in a 100-120 capsule bottle. Vorinostat will be given at 400 mg per day (4x 100 mg tablets), 4 of 7 days. Vorinostat is manufactured by Merck & Co., Inc.

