## 5.2.5 Monitoring and Toxicity Management

Each patient receiving pembrolizumab in combination with Tamoxifen and Vorinostat will be evaluable for safety. The safety parameters include all laboratory tests and hematological abnormalities, physical findings, and spontaneous reports of adverse events reported to the investigator by patients.

Each patient will be assessed periodically for the development of any toxicity as outlined in [Section 6 Study Procedures and Observations](#). Toxicity will be assessed according to the NCI CTCAE v5.0. Dose adjustments will be made according to the system showing the greatest degree of toxicity.

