### **5.4 Discontinuation and Withdrawal**

Participants may discontinue study treatment at any time for any reason or be dropped from the study treatment at the discretion of the investigator should any untoward effect occur. In addition, a participant may be discontinued from study treatment by the investigator or the Sponsor if study treatment is inappropriate, the trial plan is violated, or for administrative and/or other safety reasons. Specific details regarding procedures to be performed at study treatment discontinuation are provided in Section 6.3.2.6 – Study Procedures Restaging or Off-Study Visit.

A participant must be discontinued from study treatment but continue to be monitored in the study for any of the following reasons:

- The participant or participant's legally acceptable representative requests to discontinue study treatment
- Confirmed radiographic disease progression outlined in Section 3.5.
- Any progression or recurrence of any malignancy, or any occurrence of another malignancy that requires active treatment
- Unacceptable adverse experiences, as described in Section 7.3.5.
- The participant has a medical condition or personal circumstance which, in the opinion of the investigator and/or sponsor, placed the participant at unnecessary risk from continued administration of study treatment.
- The participant has a confirmed positive serum pregnancy test
- Noncompliance with study treatment or procedure requirements
- Recurrent Grade 2 pneumonitis
- Discontinuation of treatment may be considered for participants who have attained a confirmed complete response (CR) and have been treated for at least 8 cycles (at least 24 weeks), receiving [for monotherapy: at least 2 doses of pembrolizumab; for combination treatment: 2 cycles of the combination including 2 doses of pembrolizumab and at least 80% of the planned doses of vorinostat beyond the date when the initial CR was declared. These participants may be eligible for second-course treatment described in Section 5.3.

- The participant is lost to follow-up
- Completion of 35 treatments (approximately 2 years) with pembrolizumab. (Patients may continue vorinostat and tamoxifen.)

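### The vorinostat neutropenia table treats a third episode at ANC 0-500 more leniently than one at ANC 500-1000, the reverse of the platelet table

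*Combined protocol and SAP*

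**What the plan says.** The neutropenia table in Section 5.2 (Hematologic Toxicity) sets the next vorinostat dose by ANC band. Full dose continues at 1000 or above. The two lower bands, 500-1000 and 0-500, share three instructions: hold until grade 2 or less, restart at 300 mg, and after a second occurrence resume at 200 mg.

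The third-occurrence entries differ:

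- ANC 500-1000: "Third occurrence: remove from study"
- ANC 0-500: "Third occurrence: discuss with sponsor and principal investigator, consider omitting alternate weeks"

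The text above the table limits its reach: "dose modification will only apply if neutropenia persists for day 1, 8, and 15 of each cycle".

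The thrombocytopenia table in the same section uses the same two entries, with the discussion entry in the row for 50,000 or below and the removal entry in the row for 25,000 or below.

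Two general rules bear on the choice of action. The opening of Section 5.2 says "If more than one of these conditions applies, use the most stringent (i.e., the greatest dose reduction". Section 5.2.5 says "Dose adjustments will be made according to the system showing the greatest degree of toxicity".

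**The concern.** A dose-modification table should not become more permissive as the toxicity deepens. Here severity changes the action at only one point, and there it does so backwards. Read literally, a third episode at an ANC of 600 ends participation, and a third episode at 400 leads to a discussion that may end in restarting the drug.

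The error costs patients in both bands. The patient with the deeper neutropenia can be re-exposed. The patient with the milder neutropenia loses access to treatment without the case review offered to the sicker one. Staff who follow the table exactly will produce both outcomes, and staff who act by clinical sense in the milder row will record a deviation.

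**Working it through.** The protocol gives no statistical figure to reproduce on this point. The check compares the tables, looks for text that overrides the inverted row, and then sizes the difference in dose.

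**1. Third-occurrence actions side by side (Section 5.2)**

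| Table | Less severe row | More severe row |
|---|---|---|
| Neutropenia | ANC 500-1000: removal | ANC 0-500: discussion, perhaps alternate weeks |
| Thrombocytopenia | 50,000 or below: discussion, perhaps alternate weeks | 25,000 or below: removal |

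These are the only two vorinostat tables that print both actions, and only the neutropenia table is inverted. Two others support the direction but not the exact wording. The AST/ALT table puts removal in its worst row (above 5 x ULN) and has no third-occurrence action in the milder row. The table for other non-hematological toxicity holds and reduces at grade 3 and stops protocol therapy at grade 4.

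Both ANC rows are complete and labelled, so a fault in reading the PDF is unlikely. The protocol gives no reason for greater leniency at deeper neutropenia.

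**2. Does any other rule repair it?**

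- The most-stringent rule in Section 5.2 applies when more than one condition is met. The two ANC bands share only the value 500. An episode wholly below 500 meets only the milder instruction.
- The rule in Section 5.2.5 chooses between organ systems, not between rows of one table.
- Section 3.5 continues treatment "until progression of disease or unacceptable toxicity", and Section 5.4 lists "Unacceptable adverse experiences, as described in Section 7.3.5" as a reason to discontinue. Section 7.3.5 sets no threshold. It covers follow-up of adverse events and allows re-challenge if the investigator judges it safe and ethical. These clauses work only through judgement. They also leave the mandatory removal in the milder row untouched.

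**3. Size of the difference in dose**

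The starting schedule comes from Section 4.1.2: "Vorinostat will be given at 400 mg per day (4x 100 mg tablets), 4 of 7 days". The calculation assumes that the four-days-in-seven schedule is kept after reduction, and that 200 mg is kept after a third episode, because the row names no new dose.

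- Planned: 400 mg x 4 = 1,600 mg per week
- First reduction: 300 x 4 = 1,200 mg per week; 1,200/1,600 = 75%
- Second reduction: 200 x 4 = 800 mg per week; 800/1,600 = 50%
- Third episode at ANC 0-500, alternate weeks omitted: (800 + 0)/2 = 400 mg per week; 400/1,600 = 25%
- Third episode at ANC 500-1000: removal, 0%

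After recovery, the more severe row therefore permits 25-50% of planned vorinostat, and the less severe row permits none.

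**The case against.** The strongest reply accepts the inversion and contests its weight.

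**The entry may never be used.** The 34-patient pilot (Sections 1.3.1.2 and 1.5), from which Section 1.4 takes the dosing rationale, does not list neutropenia among its grade 2 or grade 3-4 toxicities. If that list is complete, 0 of 34 gives a one-sided 95% upper bound of 1 - 0.05^(1/34) = 8.4% for a first grade 3-4 episode. That is about 3 patients in an arm of 35 (0.084 x 35 = 2.9). The disputed entry needs a third episode after two dose reductions, and persistence on days 1, 8 and 15. This supports calling the event rare. It is no firm estimate, because Section 1.5 introduces its toxicities as ones that were included, so the list may be partial. The rate of third episodes remains unknown.

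**The lenient row does not order a restart.** Vorinostat is held until grade 2 or less, and removal is a possible result of the discussion. Section 5.4 also lets the investigator withdraw a patient, and requires treatment to stop when a medical condition creates unnecessary risk in the opinion of the investigator or sponsor. This is correct, and it narrows the gap to mandatory removal against case-by-case review. That gap still favours the more severe toxicity.

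**The most-stringent rule may reach some cases.** One episode can include counts in both bands, for example 400 and then 800. The table does not say which row then governs, or whether occurrences are counted within a row or across rows. In such mixed episodes the rule could reasonably point to removal. It does not reach an episode that stays below 500.

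**The trial's conclusions are unaffected.** Section 8.3.1 analyses efficacy in all randomized patients, so neither action changes the denominator. This stands. The point concerns safety and dose management only.

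**Conclusion.** The concern holds. The third-occurrence rule for vorinostat neutropenia is inverted with respect to severity and contradicts the platelet table, and nothing else in the protocol corrects it. The most likely explanation is two transposed entries, but that is an inference and only the sponsor can confirm it.

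The difference is 25-50% of planned weekly vorinostat after a third episode below 500, against 0% after a third episode at 500-1000, under the dose and schedule assumptions stated in the check. It applies to Arm A only, which will have 13 to 35 patients, and to an event that is probably rare. The table should be corrected because it is an operative safety rule.

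**What to change.** Ask the sponsor to confirm the intent, then exchange the two entries in the Section 5.2 neutropenia table:

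- ANC 500-1000: "Third occurrence: discuss with sponsor and principal investigator, consider omitting alternate weeks"
- ANC 0-500: "Third occurrence: remove from study"

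This matches the thrombocytopenia table. If the sponsor intends something else, the action at ANC 0-500 should still be at least as strict as the action at ANC 500-1000; removal in both rows would meet that.

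The cost is two table entries in a protocol amendment. Design, sample size and analysis do not change. The same amendment could correct a separate clerical slip that carries no weight here: the anemia table gives hemoglobin in mg/dl where g/dL is meant.
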